15 CLINICAL PHARMACOKINETIC AND PHARMACODYNAMIC ANALYSES

15.1 Pharmacokinetic Endpoints

The PK endpoints of the study are:

- Plasma concentrations of ACP-044 using sparse sampling on the following study days: Baseline (Week 0), Week 1, Week 2, and Week 4 (EOT)/ET
- ACP-044 PK parameters determined using a population PK approach

Plasma concentration of ACP-044 will be summarized by treatment group using the Pharmacokinetic Analysis Set.

PK parameter summary and analysis will be discussed in a separate plan.

15.2 Pharmacokinetic/Pharmacodynamic Endpoints

- ACP-044 exposure-response relationship:
 - for efficacy using the primary endpoint and selected secondary endpoints

- for safety using selected TEAEs

PK/PD endpoint summary and analysis will be discussed in a separate plan.

16 INTERIM ANALYSIS

No interim analyses are planned for this study.

17 DATA MONITORING/REVIEW COMMITTEE

There is no data monitoring/review committee in this study.

18 COMPUTER METHODS

Statistical analyses will be performed using Version 9.4 (or newer) of SAS® (SAS® Institute, Inc., Cary, North Carolina) on a suitably qualified and validated environment.

Validation and quality control of the tables, listings and figures containing the results of the statistical analyses will follow appropriate standard operating procedures.

19 CHANGES TO ANALYSES SPECIFIED IN PROTOCOL

Due to early termination of the ACP-044 program, the changes to the planned analyses are:

- Primary efficacy endpoint will be analyzed using an analysis of covariance model (ANCOVA) based on the FAS with treatment, sex, and baseline K-L score (randomization strata) as main factors and baseline weekly average of daily average pain score as a covariate in the model. The missing data will be imputed using baseline observed data carried forward (BOCF).
- Key secondary efficacy endpoints, the observed data will be provided in descriptive statistics including point estimates and listings.
- Secondary efficacy endpoints, the observed data will be provided in descriptive statistics and listings, no statistical inferences will be applied.
- Exploratory efficacy endpoints, the observed data will be provided in descriptive statistics and listings, no statistical inferences will be applied.

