9.5.2 Primary Analyses

The primary efficacy variable will be analyzed using an analysis of covariance model (ANCOVA) based on the FAS with treatment, sex, and baseline K-L score (randomization strata) as factors and baseline weekly average of daily average pain score as a covariate in the model. The primary comparison will be between each ACP-044 dose group versus the placebo group. The comparison between the average of the means of the two ACP-044 dose groups versus the mean of placebo group will also be conducted. Missing data will be imputed using multiple imputation based on missing at random assumption (MAR) with an exception of missing data from subjects who are treated with ACP-044 and discontinue the study due to lack of efficacy or adverse events. Their missing data will be imputed using the data from placebo group. The details of missing data imputation and multiplicity adjustment will be described in the SAP.

Sensitivity analysis using pattern mixture model and tipping point approach with multiple imputation to impute missing data will be performed to assess the robustness of the results due to treatment discontinuation and other intercurrent events.

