12.3 Handling of Missing Data

Weekly Mean Pain Intensity Scores

If a subject reports at least 3 days with non-missing pain intensity scores within a particular week, the weekly mean pain intensity score will be derived using the non-missing scores only. This is identical to imputing the missing scores as the mean of the non-missing scores. If the subject reports less than 3 days with non-missing pain intensity scores within a particular week, the weekly mean pain intensity score will be treated as missing data.

Missing weekly mean pain intensity scores will be imputed using multiple missing data and pattern mixture methodology as detailed in Section 13. Sensitivity analyses will be conducted exploring different patterns for missing data.

WOMAC Index Total Score

If at least 50% of items within a subscale are non-missing, the missing items of the WOMAC score at a weekly visit will be imputed using the mean of non-missing items within the same subscale. Otherwise, the item, the subscale score and the total score will all remain missing. The total and subscale scores will be derived as the sum of all respective observed and imputed scores. If all values of a particular subscale are missing at a particular week then the total and corresponding subscale score will be treated as missing.

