13 METHODS OF EFFICACY ANALYSES

13.1 Primary Efficacy Endpoints

13.1.1 Primary Efficacy Endpoints

Estimand

The primary estimand has the following attributes:

- Population: all randomized subjects who received at least one dose of study drug and with baseline pain assessments and at least one post-baseline pain assessment.
- Endpoint: change from baseline to week 4 in the average of the daily average Numeric Rating Scale (NRS) pain intensity scores
- Intercurrent events: premature discontinuation from the study, the hypothetical estimand is to evaluate the pharmacological effect as if no withdrawals had occurred.
- Treatment condition: one of the randomized treatment groups of the following per protocol: 1600 mg total dose (provided as 2×800 mg tablets), 1600 mg total dose (provided as 4×400 mg tablets), or placebo.
- Population-level summary: difference in mean of endpoint between treatment conditions.

Statistical Hypotheses

The primary endpoint is the change from baseline to week 4 in the average of the daily average Numeric Rating Scale (NRS) pain intensity scores.

The mean change from baseline to week 4 daily average NRS score will be compared between each of the ACP-044 dose groups (400 mg QID, 800 mg BID) to the placebo group.

The null hypothesis is the mean change from baseline to week 4 in the average of the daily average Numeric Rating Scale (NRS) pain intensity scores using ACP-044 is equal to that of placebo in subjects with pain associated with osteoarthritis of the knee.

The alternative hypothesis is the mean change from baseline to week 4 in the average of the daily average Numeric Rating Scale (NRS) pain intensity scores using ACP-044 is not equal to that of placebo in subjects with pain associated with osteoarthritis of the knee.

Primary Estimator

The primary efficacy variable will be analyzed using an analysis of covariance model (ANCOVA) based on the FAS with treatment, sex, and baseline K-L score (randomization strata) as factors and baseline weekly average of daily average pain score as a covariate in the model. The primary comparison will be between each ACP-044 dose group versus the

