placebo group. The comparison between the average of the means of the two ACP-044 dose groups versus the mean of placebo group will also be conducted. Missing data will be imputed using multiple imputation based on missing at random assumption (MAR) with an exception of missing data from subjects who are treated with ACP-044 and discontinue the study due to lack of efficacy or adverse events. Their missing data will be imputed using the data from placebo group.

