13.1.2 Sensitivity Analyses

No sensitivity analyses are planned for primary efficacy endpoint.

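### SAP section 19 switches the primary analysis to BOCF but leaves the as-if-no-withdrawals estimand in place, so the only primary analysis does not match its stated target

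*SAP*

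**What the plan says.** The SAP contains three statements on missing primary data.

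- **Section 12.3:** "Missing weekly mean pain intensity scores will be imputed using multiple missing data and pattern mixture methodology as detailed in Section 13". It adds: "Sensitivity analyses will be conducted exploring different patterns for missing data".
- **Section 13.1.1:** multiple imputation under missing at random (MAR), except for ACP-044 subjects who stop for lack of efficacy or an adverse event (AE). For those, "Their missing data will be imputed using the data from placebo group".
- **Section 19:** "The missing data will be imputed using baseline observed data carried forward (BOCF". The reason given is early termination of the program.

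The estimand in section 13.1.1 handles its one intercurrent event as follows: "premature discontinuation from the study, the hypothetical estimand is to evaluate the pharmacological effect as if no withdrawals had occurred". Section 19 does not revise this.

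Protocol 9.5.2 promises: "Sensitivity analysis using pattern mixture model and tipping point approach with multiple imputation to impute missing data will be performed". SAP 13.1.2 states: "No sensitivity analyses are planned for primary efficacy endpoint". Section 19 does not list that as a change.

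Appendix B of the SAP shows a single version, 1.0, dated 21 September 2022. That is 44 days after the termination date of 8 August 2022 given in the Introduction, so all these statements were issued together after the trial had stopped.

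**The concern.** BOCF assigns zero change to every missing Week 4 score. That is not an estimate of what the subject would have scored without withdrawing.

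It fits the stated reason for the change especially badly. A Week 4 value lost only because the sponsor stopped the trial carries no information about drug response, yet it is scored as no improvement. The same happens to a subject who completed treatment but kept too few diary entries. Section 12.3 makes the weekly mean missing in this case: "If the subject reports less than 3 days with non-missing pain intensity scores within a particular week". BOCF also ignores the diary data already collected, although membership of the Full Analysis Set requires at least one pain score after baseline.

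The primary ANCOVA is the only efficacy analysis for which section 19 keeps a model. If its estimate is shifted, no planned sensitivity analysis would show by how much.

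**Working it through.** **Inputs from the documents (SAP 1 and 3.5).** Design difference 0.85, written here as d = −0.85 (negative favours ACP-044); SD 1.7; two-sided alpha 0.05; 20% discontinuation; 61 subjects randomized at termination.

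**Assumed, not in the documents.** Mean placebo change m = −1.5, with a range of −1.0 to −2.0; all missing shares other than the 20% planning rate; missingness unrelated to outcome within an arm.

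**The plan's own figure.** The normal approximation gives n = 2 × (1.96 + 0.8416)² × (1.7/0.85)² = 62.8, so 63 per arm. The exact t calculation gives 64, with power 0.801. Then 64/0.80 = 80 per arm and 3 × 80 = 240. The stated sample size is reproduced.

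**Expected BOCF estimate.** With missing shares fA (active) and fP (placebo):

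E = (1 − fA)(m + d) − (1 − fP)m

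When fA = fP = f this reduces to (1 − f)d, whatever m is. At 20%: 0.80 × (−0.85) = −0.68. As an example of unequal loss, 25%/15% at m = −1.5 gives 0.75 × (−2.35) − 0.85 × (−1.5) = −1.7625 + 1.275 = −0.49.

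| Missing, active/placebo | m = −1.0 | m = −1.5 | m = −2.0 |
|---|---|---|---|
| 20%/20% | −0.68 | −0.68 | −0.68 |
| 30%/30% | −0.60 | −0.60 | −0.60 |
| 25%/15% | −0.54 | −0.49 | −0.44 |
| 15%/25% | −0.82 | −0.87 | −0.92 |
| 10%/30% | −0.97 | −1.07 | −1.17 |

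**When BOCF exaggerates the effect.** This needs fP/fA > (|m| + |d|)/|m|. At m = −1.5 that is 2.35/1.5 = 1.57 (1.85 at m = −1.0, 1.43 at m = −2.0).

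**No true effect.** E = m(fP − fA). Each 10-point gap in missingness shifts the estimate by 0.15 (0.10 to 0.20) against the arm with more missing data. Balanced missingness gives no shift.

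**Comparison with the 13.1.1 rule.** If AE and lack-of-efficacy dropouts on active (share gA) are imputed fully at placebo level and the rest under MAR, the expected estimate is d(1 − gA). With 10% such dropouts plus 10% other missing in each arm, this is −0.85 × 0.90 = −0.765, against −0.68 for BOCF. If all 20% were AE or lack of efficacy and balanced, both rules give −0.68. The gap therefore comes from other missing data, such as termination, and from unequal missingness.

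**Simulation.** 1,500 replicates per scenario; arms of 21, 20 and 20; SD 1.7; weekly correlation 0.75; 0 to 3 weeks observed before dropout; ANCOVA with treatment, sex, K-L score and baseline; 15 imputations combined by Rubin's rules. The Monte Carlo standard error of each mean is about 0.015.

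| AE or lack of efficacy, active/placebo | Other missing per arm | BOCF | 13.1.1 rule |
|---|---|---|---|
| 10%/10% | 0% | −0.76 | −0.79 |
| 10%/10% | 10% | −0.66 | −0.78 |
| 10%/10% | 20% | −0.60 | −0.79 |
| 15%/5% | 10% | −0.47 | −0.76 |
| 5%/15% | 10% | −0.85 | −0.80 |
| 15%/5%, no true effect | 10% | +0.18 | +0.02 |
| 5%/15%, no true effect | 10% | −0.14 | 0.00 |

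In the second row, power is 21% for BOCF and 20% for the 13.1.1 rule. In the two null rows BOCF rejects 5.4% to 5.8% of the time. In a separate simulation with 20 per arm and no true effect, a more extreme 30%/10% split raised rejection to about 9%.

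A repeat with the imputation model fitted across arms gave −0.70 for BOCF and −0.80 for multiple imputation in the second row, −0.48 and −0.76 in the fourth, and +0.17 and +0.03 in the sixth. The standard error of multiple imputation was about 6% to 14% higher.

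**The case against.** **Section 19 governs.** It is headed as a list of changes, gives a reason and restates the whole primary model, so an analyst would know to run BOCF. That is right, and it reduces the conflict with sections 12.3 and 13.1.1 to leftover text. It does not repair the estimand or the incomplete list of changes.

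**The mismatch predates BOCF.** The placebo-based exception in 13.1.1 does not target an outcome without withdrawals either. This also stands. Restoring 13.1.1 unchanged would not give full alignment, so the estimand wording has to change as well. Rewording the estimand to fit BOCF would be another way to remove the mismatch.

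**The practical effect may be small.** With balanced missingness power hardly differs. Root mean squared error against −0.85 was 0.563 for BOCF and 0.560 for multiple imputation, because the added variance offsets the removed bias. With more AE or lack-of-efficacy dropout on active (15%/5%), multiple imputation is better (0.57 against 0.67); with the reverse, BOCF is marginally better (0.54 against 0.55). The documents favour none of these patterns. But in a trial of 61 subjects the estimate is likely to be read more than the p-value, and the estimate is what shifts.

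**There are partial checks.** Discontinuations are tabulated by arm and reason, all data are listed, and observed responder rates on the same score are summarised. These show how much is missing and why, but not what the imputation does to the primary estimate.

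**Conclusion.** The concern holds. The mismatch between estimand and estimator, the contradiction between sections 12.3 and 13.1.2, and the undeclared loss of the protocol's sensitivity analyses are plain from the text and do not depend on any missing rate.

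The size of the bias does depend on it. BOCF is unbiased if nothing is missing, or if there is no true effect and missingness is balanced. Otherwise, at the design effect, balanced loss shrinks the estimate by the missing fraction (20% loss turns −0.85 into −0.68). More loss on active works against the drug. Clearly more loss on placebo inflates the effect, so BOCF cannot be relied on as conservative. The harm is bias rather than lost power. The actual missing shares by arm and reason are not in the documents, the share due to termination could be zero, and the placebo change of −1.5 is assumed.

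**What to change.** In section 19:

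- Keep the 13.1.1 multiple imputation as the primary method, using baseline and the Week 1 to 3 averages. Fit it across arms with treatment as a predictor, because arms have only about 20 subjects.
- Treat all missing data not due to AE or lack of efficacy as MAR, including those due to termination. Protocol 4.5 already lists sponsor termination as a discontinuation reason, so these subjects can be identified.
- Keep BOCF at most as a sensitivity analysis.
- List every protocol sensitivity analysis that is dropped.

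Elsewhere, make sections 12.3, 13.1.1 and 13.1.2 agree with section 19, and word the estimand so that it is consistent with the placebo-based rule for AE and lack-of-efficacy discontinuations. If the sponsor prefers BOCF as primary, the minimum is to restate the estimand to match it.

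The cost is SAP wording, which should be settled before treatment codes are released (the documents do not say whether that has happened), and a little more programming. The standard error rises by about 10% (0.61 against 0.555 in the simulation at 20% missing), and power does not improve when missingness is balanced.

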21 APPENDICES

Appendix A Schedule of Events and Assessments

	Screening Period	Baseline Pain Assessment Period	Double-Blind Treatment Period								Safety Follow-up Period	
			Baseline Week 0	Day 3	Week 1	Week 2	Week 3	Week 4	Unscheduled Visit ^r		Clinic visit	Telephone call
Visit Day/Week	Days -35 to -8	Days -7 to -1								7 days after EOT	30 days after last dose	
Visit Number	1	2	3	4	5	6	7	8 (EOT/ET)				
Visit window (# days)		+3	0	±1	±3	±3	±3	±3		±3		+4
Informed consent	X											
Inclusion/exclusion criteria	X	X	X									
Medical, medication, and surgical history and demographics	X											
Physical examination	X		X						X			
Vital signs (including orthostatic changes) ^a	X	X	X		X	X			X	X		
Height, weight, and BMI calculation ^b	X		X						X			
12-lead ECG ^c	X		X ^c		X	X			X			
Clinical laboratory tests	X		X	X ^d	X	X	X ^d	X				
Pregnancy test ^e	X		X						X			
Urine drug screen	X	X	X ^f						X			
COVID-19 test ^g	X											
C-SSRS	X	X	X		X	X			X	X		
Beck Depression Inventory-II	X											
Verified Clinical Trials Subject Registry	X											
Central Imagingh	X											
Issue eDiary and train on usei		X										
Collect eDiary									X			

Appendix A Schedule of Events and Assessments (Continued)

	Screening Period	Baseline Pain Assessment Period	Double-Blind Treatment Period							Unscheduled Visit ^r	Safety Follow-up Period	
			Baseline Week 0	Day 3	Week 1	Week 2	Week 3	Week 4			Clinic visit	Telephone call
Visit Day/Week	Days -35 to -8	Days -7 to -1									7 days after EOT	30 days after last dose
Visit Number	1	2	3	4	5	6	7	8 (EOT/ET)				
Visit window (# days)		+3	0	±1	±3	±3	±3	±3		±3		+4
Randomization			X									
PK blood sample collection ^j			X ^k		X ^l	X ^l		X ^l				
eDiary completion: Numeric Rating Scale Daily Pain Score (Average and Worst) ^m		X	X	X	X	X	X	X		X		
PGIC ⁿ					X	X		X				
WOMAC ⁿ				X	X	X		X				
BPI-sf ⁿ			X		X	X		X				
SF-12			X						X			
HADS	X		X						X			
Participant Scorecard ^o					X	X		X				
Accurate Symptom Reporting (ASR) Training – subject facing	X		X		X ^p	X ^p		X ^p				
Placebo Response Reduction (PRR) Training – subject facing	X		X		X ^p	X ^p		X ^p				
Study drug dispensing/accountability			X		X	X			X			
eDiary completion: Rescue medication dispensing/accountability ^q		X	X	X	X	X	X	X				
Prior and concomitant medications	X	X	X	X	X	X	X	X	X	X	X	X
Assessment of adverse events	X	X	X	X	X	X	X	X	X	X	X	X

Abbreviations: ASR=accurate symptom reporting; BMI=body mass index; BPI-sf=Brief Pain Inventory–Short Form; COVID-19=coronavirus disease 2019; C-SSRS=Columbia–Suicide Severity Rating Scale; ECG=electrocardiogram; eDiary=electronic diary; EOT=end of treatment; ET=early termination; HADS=Hospital Anxiety and Depression Scale; PGIC=Subject Global Impression of Change; PK=pharmacokinetic; PRR=placebo response reduction; SF-12=12-item Short Form Survey; WOMAC=Western Ontario and McMaster Universities Osteoarthritis Index

- ^a Vital signs will include body temperature, resting respiration rate, supine and standing systolic and diastolic blood pressure, and pulse rate. Blood pressure and pulse rate will be measured after the subject rests for 5 minutes in the supine position. The subject will then be asked to stand and blood pressure and pulse rate will be taken after standing for 1 minute and then again after 3 minutes. Subjects unable to stand may be assessed while sitting upright. The same position and arm should be used each time vital signs are measured for a given subject.
- ^b Height will only be measured at the Screening visit, and BMI will be calculated based on height and weight measurements at Screening. Weight will also be measured at any unscheduled visit.
- ^c A single 12-lead ECG will be performed at Screening, at Baseline (Week 0) both predose and at 1 hour postdose (the first dose of the day), Week 1, Week 2, and EOT/ET. A 1-hour window is permitted for the predose ECG and a 20-minute window is permitted for the postdose ECGs. Electrocardiograms should be performed before blood sampling or at least 30 minutes after blood sampling.
- ^d A full chemistry (CHEM) panel of clinical laboratory tests will be completed, excluding glucose and the CHEM tests noted in Section 6.5.5 to only be performed at Screening.
- ^e Applicable to women of childbearing potential. A serum pregnancy test should be performed at Screening and a urine test must be performed at all other designated visits.
- ^f At Baseline, urine drug screen will be performed using a dipstick test which must be negative for any non-permitted medications or drugs in order for the subject to continue in the study.
- ^g COVID-19 diagnostic PCR test at Screening.
- ^h Randomization visit cannot occur until there is confirmation from the central reader that there are no exclusionary findings.
- ⁱ Subjects will be instructed on the use of and will complete electronic clinical outcome assessments using handheld devices during the study. An eDiary, will be used to record pain scores, compliance with ingestion of study medication, and use of rescue medication.
- ^j A PK sample (approximately 4 mL) should also be taken from subjects who experience SAEs or AEs leading to discontinuation, as soon as possible after the occurrence of the event.
- ^k A predose PK blood sample must be collected before administration of study drug. A postdose PK blood sample will be collected at the end of ECG assessment approximately 1 hour after study drug administration.
- ^l PK samples at Visits 5, 6, and 8 will be collected at one of the following time intervals: 1) 2-5 hours after morning dosing OR 2) 6-9 hours after morning dosing OR 3) 10-12 hours after morning dosing. Every effort should be made to collect the PK samples at distinct time intervals during Visits 5, 6, and 8. However, if the interval is the same across these visits, then the collection time should vary within that interval.
- ^m Pain intensity assessments are to be recorded in the evening during the Baseline Assessment Period and prior to their 4th dose of the day during the Double-blind period. Subjects will be rating both the average daily pain as well as their worst daily pain. At the Safety Follow-up Clinic Visit (7 days after EOT), subjects will rate both the average daily pain as well as their worst daily pain over the past week and the data will be entered into EDC.
- ⁿ At study visits, PGIC, WOMAC, and BPI-sf should be performed before blood sample collection, ECG, and other procedures.

- o Participant Scorecard is viewed by the subject and reviewed by the Investigator at the designated study visits. The Investigator or designee, will acknowledge the scorecard review on the training platform, aLearn.
- p ASR and PPR training at Visits 5, 6, and/or 8 is on an as needed basis and the need for training will be determined by Participant Scorecard intervention recommendations.
- q Record rescue medication use in eDiary.
- r The Investigator may perform any additional evaluations deemed to be clinically indicated. If an unscheduled visit is required for safety reasons, a 12-lead ECG and all appropriate clinical laboratory tests are to be performed.

